7.1.1. Packaging and Labeling

Dulaglutide will be supplied by Lilly as a 3.0-mg/mL solution in PFS (Trulicity® USPI 2017) and as a 9.0-mg/mL solution in SDP. Both the PFS and the SDP should be stored refrigerated (2°C to 8°C) and allowed to warm to room temperature for at least 30 minutes (up to 24 hours) prior to use.

The investigational product will be labeled according to the country's regulatory requirements.

7.1.2. Drug Delivery Devices

The manufactured medical devices provided for use in the study include a PFS containing 1.5 mg dulaglutide (0.5 mL at 3.0 mg/mL) and a SDP containing 4.5 mg dulaglutide (0.5 mL at 9.0 mg/mL).

The medical devices will be labeled according to the country's regulatory requirements.

7.2. Method of Treatment Assignment

Eligible subjects will be randomized to 1 of the 2 treatment sequences (Table GBGM.3). Randomization tables will be prepared by the statistician or designee for the study and provided to the site pharmacists involved in dose preparation. The allocation and dispensing of the investigational product will be fully documented and verified by a second person. Detailed records of the amounts of the investigational product received, dispensed, and remaining at the end of the study will be maintained by the site pharmacist.

Approximately the same number of subjects will be randomized to each treatment sequence.

Table GBGM.3. Treatment Sequences

| Treatment Sequence | Period 1 | Period 2 |
|--------------------|-------------------|-------------------|
| 1 | Prefilled Syringe | Single Dose Pen |
| 2 | Single Dose Pen | Prefilled Syringe |

7.2.1. Selection and Timing of Doses

The doses will be administered according to the randomization schedule at approximately the same times on each day. The actual time of all dose administrations will be recorded in the subject's electronic case report form (eCRF).

Prior to dulaglutide dosing, subjects will be fasted for approximately 8 hours and a standard breakfast will be provided approximately 15 minutes after dosing.

7.3. Blinding

This is an open-label study due to the objective nature of the PK data and the different appearance, shape, size, and functionality of the devices.

7.4. Dose Modification

Dose adjustments are not allowed in this study.

7.4.1. Special Treatment Considerations

If a device malfunctions before the needle is inserted (i.e., unable to activate the device, unable to unlock and/or unable to pull the needle shield), a replacement will be given. If the device malfunctions during the injection process (e.g., needle did not retract), the device will not be replaced, and all planned assessments will continue. The investigator or designee will fill out a

complaint form, collect the associated device, submit the complaint form, and return the suspect device to Lilly.

7.5. Preparation/Handling/Storage/Accountability

Both the PFS and the SDP should be stored refrigerated (2°C to 8°C) and allowed to warm to room temperature for at least 30 minutes (up to 24 hours) prior to use.

The investigator or designee must confirm appropriate temperature conditions have been maintained, as communicated by sponsor, during transit for all investigational product received and any discrepancies are reported and resolved before use of the study treatment.

Only participants enrolled in the study may receive investigational product or study materials, and only authorized site staff may supply or administer investigational product. All investigational products should be stored in an environmentally controlled and monitored (manual or automated) area in accordance with the labeled storage conditions with access limited to the investigator and authorized site staff.

The investigator, institution, or the head of the medical institution (where applicable) is responsible for study treatment accountability, reconciliation, and record maintenance (such as receipt, reconciliation, and final disposition records).

At the end of the study, and with agreement from Lilly, both used and unused PFSs and SDPs, with the exception of a product complaint, may be destroyed by a qualified vendor.

7.6. Treatment Compliance

The investigational product will be administered at the clinical site, and documentation of treatment administration will occur at the site.

7.7. Concomitant Therapy

With the exception of vitamin/mineral supplements and/or HRT, prescription medications are not to be taken from 14 days prior to drug administration and throughout the study.

Over-the-counter medications other than acetaminophen are not to be taken from 7 days prior to drug administration and throughout the study. The use of topical medication may be permitted if no evidence of chronic dosing with the risk of systemic absorption exists.

In general, concomitant medication should be avoided; however, acetaminophen (1 g, maximum 4 g per 24 hours) may be administered at the discretion of the investigator for treatment of headaches, etc. If the need for concomitant medication (other than acetaminophen) arises, inclusion or continuation of the subject may be at the discretion of the investigator after consultation with a Lilly Clinical Pharmacologist (CP) or Clinical Research Physician (CRP). Any medication used during the course of the study must be documented.

7.8. Treatment after the End of the Study

Not applicable for this study.

8. Discontinuation Criteria

Subjects discontinuing from the treatment/study prematurely for any reason should complete AE and other follow-up procedures per Section 2 of this protocol.

8.1. Discontinuation from Study Treatment

If the subject has an elevated amylase and/or lipase value, or is suspected of having pancreatitis, please refer to the pancreatic safety monitoring algorithm ([Appendix 6](#)).

Discontinuation of the investigational product for abnormal liver tests **should be considered** by the investigator when a subject meets 1 of the following conditions after consultation with the Lilly designated medical monitor:

- Alanine aminotransferase (ALT) or aspartate aminotransferase (AST) $>5\times$ upper limit of normal (ULN)
- ALT or AST $>3\times$ ULN sustained for more than 2 weeks, or
- ALT or AST $>3\times$ ULN and total bilirubin level (TBL) $>2\times$ ULN or international normalized ratio >1.5 , or
- ALT or AST $>3\times$ ULN with the appearance of fatigue, nausea, vomiting, right upper-quadrant pain or tenderness, fever, rash, and/or eosinophilia ($>5\%$)
- Alkaline phosphatase (ALP) $>3\times$ ULN
- ALP $>2.5\times$ ULN and TBL $>2\times$ ULN
- ALP $>2.5\times$ ULN with the appearance of fatigue, nausea, vomiting, right quadrant pain or tenderness, fever, rash, and/or eosinophilia ($>5\%$)

8.1.1. Discontinuation of Inadvertently Enrolled Subjects

If the sponsor or investigator identifies a subject who did not meet enrollment criteria and was inadvertently enrolled, a discussion must occur between the Lilly CP/CRP and the investigator to determine if the subject may continue in the study. If both agree it is medically appropriate to continue, the investigator must obtain documented approval from the Lilly CP/CRP to allow the inadvertently enrolled subject to continue in the study with or without continued treatment with investigational product.

8.2. Discontinuation from the Study

Subjects will be discontinued in the following circumstances:

- Enrollment in any other clinical study involving an investigational product or enrollment in any other type of medical research judged not to be scientifically or medically compatible with this study
- Participation in the study needs to be stopped for medical, safety, regulatory, or other reasons consistent with applicable laws, regulations, and good clinical practice

- Investigator Decision
 - the investigator decides that the subject should be discontinued from the study
- Subject Decision
 - the subject, or legal representative, requests to be withdrawn from the study

8.3. Subjects Lost to Follow-up

A subject will be considered lost to follow-up if he or she repeatedly fails to return for scheduled visits and is unable to be contacted by the study site. Site personnel are expected to make diligent attempts to contact subjects who fail to return for a scheduled visit or were otherwise unable to be followed up by the site.

9. Study Assessments and Procedures

Section 2 lists the Schedule of Activities, detailing the study procedures and their timing.

Appendix 2 lists the clinical laboratory tests that will be performed for this study.

Appendix 5 provides a summary of the maximum number and volume of invasive samples, for all sampling, during the study.

Unless otherwise stated in subsections below, all samples collected for specified laboratory tests will be destroyed within 60 days of receipt of confirmed test results. Certain samples may be retained for a longer period, if necessary, to comply with applicable laws, regulations, or laboratory certification standards.

9.1. Efficacy Assessments

This section is not applicable for this study.

9.2. Adverse Events

Investigators are responsible for monitoring the safety of subjects who have entered this study and for alerting Lilly or its designee to any event that seems unusual, even if this event may be considered an unanticipated benefit to the subject.

The investigator is responsible for the appropriate medical care of subjects during the study.

Investigators must document their review of each laboratory safety report.

The investigator remains responsible for following, through an appropriate health care option, AEs that are serious or otherwise medically important, considered related to the investigational product or the study, or that caused the subject to discontinue the investigational product before completing the study. The subject should be followed until the event resolves, stabilizes with appropriate diagnostic evaluation, or is reasonably explained. The frequency of follow-up evaluations of the AE is left to the discretion of the investigator.

After the informed consent form is signed, study site personnel will record, via eCRF, the occurrence and nature of each subject's preexisting conditions, including clinically significant signs and symptoms of the disease under treatment in the study. Additionally, site personnel will record any change in the condition(s) and the occurrence and nature of any AEs.

The investigator will interpret and document whether or not an AE has a reasonable possibility of being related to study treatment, study device, or a study procedure, taking into account the disease, concomitant treatment, or pathologies.

A "reasonable possibility" means that there is a potential cause and effect relationship between the investigational product, study device, and/or study procedure and the AE.

Planned surgeries should not be reported as AEs unless the underlying medical condition has worsened during the course of the study.

If a subject's investigational product is discontinued as a result of an AE, study site personnel must report this to Lilly or its designee via eCRF.

9.2.1. Serious Adverse Events

An SAE is any AE from this study that results in one of the following:

- death
- initial or prolonged inpatient hospitalization
- a life-threatening experience (i.e., immediate risk of dying)
- persistent or significant disability/incapacity
- congenital anomaly/birth defect
- important medical events that may not be immediately life-threatening or result in death or hospitalization but may jeopardize the subject or may require intervention to prevent one of the other outcomes listed in the definition above
- when a condition related to the SDP or PFS necessitates medical or surgical intervention to preclude either permanent impairment of a body function or permanent damage to a body structure, the serious outcome of "required intervention" will be assigned

Study site personnel must alert the Lilly CRP/CP, or its designee, of any SAE as soon as practically possible.

Additionally, study site personnel must alert Lilly Global Patient Safety, or its designee, of any SAE within 24 hours of investigator awareness of the event via a sponsor-approved method. If alerts are issued via telephone, they are to be immediately followed with official notification on study-specific SAE forms. This 24-hour notification requirement refers to the initial SAE information and all follow-up SAE information.

Although all AEs are recorded in the eCRF after signing informed consent, SAE reporting to the sponsor begins after the subject has signed informed consent and has received investigational product. However, if an SAE occurs after signing informed consent, but prior to receiving investigational product, AND is considered Reasonably Possibly Related to a study procedure then it MUST be reported.

Investigators are not obligated to actively seek AEs or SAEs in subjects once they have discontinued from and/or completed the study (the subject summary eCRF has been completed). However, if the investigator learns of any SAE, including a death, at any time after a subject has been discharged from the study, and the investigator considers the event reasonably possibly related to the study treatment or study participation, the investigator must promptly notify Lilly.

Pregnancy (maternal or paternal exposure to investigational product) does not meet the definition of an AE. However, to fulfill regulatory requirements any pregnancy should be reported following the SAE process to collect data on the outcome for both mother and fetus.

9.2.1.1. Suspected Unexpected Serious Adverse Reactions

Suspected unexpected serious adverse reactions (SUSARs) are serious events that are not listed in the IB and that the investigator reports as related to investigational product or procedure. Lilly has procedures that will be followed for the recording and expedited reporting of SUSARs that are consistent with global regulations and the associated detailed guidances.

9.2.2. Complaint Handling

Lilly collects product complaints on investigational products and drug delivery systems used in clinical trials in order to ensure the safety of study participants, monitor quality, and to facilitate process and product improvements.

Subjects should be instructed to contact the investigator as soon as possible if he or she has a complaint or problem with the investigational product or drug delivery system so that the situation can be assessed.

9.3. Treatment of Overdose

Effects of overdose with dulaglutide in clinical studies have included gastrointestinal disorders and hypoglycemia. In the event of overdose, appropriate supportive treatment (including frequent plasma glucose monitoring) should be initiated according to the subject's clinical signs and symptoms.

Refer to the IB and Trulicity® USPI (2017).

9.4. Safety

9.4.1. Laboratory Tests

For each subject, clinical laboratory tests detailed in [Appendix 2](#) should be conducted according to the Schedule of Activities (Section 2) and as clinically indicated. Clinical laboratory assessments will include amylase and lipase.

9.4.1.1. Amylase and Lipase Tests

Serum amylase and lipase measurements will be collected as part of the clinical laboratory testing as well as at time points specified in the Schedule of Activities (Section 2). Where indicated in the Schedule of Activities, amylase and lipase results must be reviewed by the study physician prior to dulaglutide dosing on subsequent days. Additional measurements may be performed at the investigator's discretion. Further diagnostic assessments will be recommended whenever lipase and/or amylase is/are confirmed to be $\geq 3 \times$ ULN at any visit post randomization, even if the subject is asymptomatic (as per the algorithm for the monitoring of pancreatic events in [Appendix 6](#), and if pancreatitis is confirmed, the case will be further defined during an adjudication process).

9.4.2. Vital Signs

For each subject, vital sign measurements should be conducted according to the Schedule of Activities (Section 2).

Blood pressure and pulse rate should be measured after at least 5 minutes supine.

Unscheduled orthostatic vital signs should be assessed, if possible, during any AE of dizziness or posture-induced symptoms. If orthostatic measurements are required, subjects should be supine for at least 5 minutes and stand for at least 2 minutes. If the subject feels unable to stand, supine vital signs only will be recorded. Additional vital signs may be measured during each study period if warranted.

9.4.3. *Electrocardiograms*

For each subject, a single 12-lead digital ECG will be collected according to the Schedule of Activities (Section 2). Electrocardiograms must be recorded before collecting any blood samples. Subjects must be supine for at least 5 minutes before ECG collection and remain supine but awake during ECG collection. Electrocardiograms may be obtained at additional times, when deemed clinically necessary. All ECGs recorded should be stored at the investigational site.

Electrocardiograms will be interpreted by a qualified physician (the investigator or qualified designee) at the site as soon after the time of ECG collection as possible, and ideally while the subject is still present, to determine whether the subject meets entry criteria at the relevant visit(s) and for immediate subject management, should any clinically relevant findings be identified.

If a clinically significant finding is identified (including, but not limited to, changes in QT interval or corrected QT interval from baseline) after enrollment, the investigator will determine if the subject can continue in the study. The investigator, or qualified designee, is responsible for determining if any change in subject management is needed, and must document his/her review of the ECG printed at the time of collection. Any new clinically relevant finding should be reported as an AE.

9.4.4. *Physical Examination*

Physical examinations and routine medical assessments will be conducted as specified in the Schedule of Activities (Section 2) and as clinically indicated.

9.4.5. *Body Weight*

Body weight will be recorded as specified in the Schedule of Activities (Section 2) and as clinically indicated.

9.4.6. *Injection Site Reactions*

Local tolerability at the injection site will be evaluated for erythema, induration, pain, pruritus, rash, and edema as indicated in Section 2 and reported in the eCRF. If one or more symptom(s) of an injection site reaction (ISR) is reported during the assessment, a single AE for ISR will be recorded on the AE page of the eCRF.

9.4.7. Safety Monitoring

The Lilly CP or CRP/scientist will monitor safety data throughout the course of the study.

Lilly will review SAEs within time frames mandated by company procedures. The Lilly CP or CRP will periodically review the following data:

- trends in safety data
- laboratory analytes including lipase and amylase
- AEs including monitoring of ISRs

When appropriate, the Lilly CP or CRP will consult with the functionally independent Global Patient Safety therapeutic area physician or clinical research scientist.

9.4.7.1. Hepatic Safety

If a study subject experiences elevated ALT $\geq 3 \times$ ULN, ALP $\geq 2 \times$ ULN, or elevated TBL $\geq 2 \times$ ULN, liver tests ([Appendix 4](#)) should be repeated within 3 to 5 days including ALT, AST, ALP, TBL, direct bilirubin, gamma-glutamyl transferase, and creatinine kinase to confirm the abnormality and to determine if it is increasing or decreasing. If the abnormality persists or worsens, clinical and laboratory monitoring should be initiated by the investigator based on consultation with the Lilly CP or CRP. Monitoring should continue until levels normalize and/or are returning to approximate baseline levels.

Additional safety data should be collected if 1 or more of the following conditions occur:

- elevation of serum ALT to $\geq 5 \times$ ULN on 2 or more consecutive blood tests
- elevated serum TBL to $\geq 2 \times$ ULN (except for cases of known Gilbert's syndrome)
- elevation of serum ALP to $\geq 2 \times$ ULN on 2 or more consecutive blood tests
- subject discontinued from treatment due to a hepatic event or abnormality of liver tests
- hepatic event considered to be an SAE

9.5. Pharmacokinetics

At the visits and times specified in the Schedule of Activities (Section 2), venous blood samples of approximately 4 mL each will be collected to determine the plasma concentrations of dulaglutide. Instructions for the collection and handling of blood samples will be provided by the sponsor. The actual date and 24-hour clock time of each dose and PK sampling will be recorded.

9.5.1. Bioanalysis

Samples will be analyzed at a laboratory approved by the sponsor and stored at a facility designated by the sponsor.

Concentrations of dulaglutide will be assayed using a validated radioimmunoassay method.

Bioanalytical samples collected to measure investigational product concentrations will be retained for a maximum of 1 year following last subject visit for the study.

9.6. Pharmacodynamics

9.6.1. Immunogenicity Assessments

At the visits and times specified in the Schedule of Activities (Section 2), venous blood samples of approximately 10 mL each will be collected to determine antibody production against dulaglutide. Additional samples may be collected if there is a possibility that an AE is immunologically mediated.

Immunogenicity will be assessed by a validated assay designed to detect anti-drug antibodies (ADA) in the presence of dulaglutide at a laboratory approved by the sponsor. Antibodies may be further characterized and/or evaluated for their ability to neutralize the activity of dulaglutide.

Samples will be retained for a maximum of 15 years after the last subject visit, or for a shorter period if local regulations and ethical review boards (ERBs) allow, at a facility selected by the sponsor. The duration allows the sponsor to respond to future regulatory requests related to dulaglutide. Any samples remaining after 15 years will be destroyed.

9.7. Genetics

A blood sample will be collected for pharmacogenetic analysis as specified in the Schedule of Activities (Section 2), where local regulations allow.

Samples will not be used to conduct unspecified disease or population genetic research either now or in the future. Samples will be used to investigate variable exposure or response to dulaglutide and to investigate genetic variants thought to play a role in insulin glucose homeostasis. Assessment of variable response may include evaluation of AEs or differences in efficacy.

All samples will be coded with the subject number. These samples and any data generated can be linked back to the subject only by the investigative site personnel.

Samples will be retained for a maximum of 15 years after the last subject visit, or for a shorter period if local regulations and/or ERBs impose shorter time limits, for the study at a facility selected by Lilly or its designee. This retention period enables use of new technologies, response to regulatory questions, and investigation of variable response that may not be observed until later in the development of dulaglutide or after dulaglutide is commercially available.

Molecular technologies are expected to improve during the 15-year storage period and therefore cannot be specifically named. However, existing approaches include whole genome or exome sequencing, genome wide association studies, multiplex assays, and candidate gene studies. Regardless of technology utilized, data generated will be used only for the specific research scope described in this section.

9.8. Biomarkers

This section is not applicable for this study.

9.9. Health Economics

This section is not applicable for this study.

10. Statistical Considerations and Data Analysis

10.1. Sample Size Determination

Approximately 24 subjects may be enrolled in order that at least 18 subjects complete the study. The sample size was based on a within-subject variability (coefficient of variation) of 21% for AUC and C_{\max} of dulaglutide from previous studies. Eighteen subjects will provide a 90% probability that the half-width of the 90% confidence interval (CI) of the ratio of the geometric means for AUC and C_{\max} is no larger than 14%.

Subjects who are randomized may be replaced to ensure that at least 18 subjects may complete the study.

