7. SAMPLE SIZE JUSTIFICATION

Approximately 24 subjects may be enrolled in order that at least 18 subjects complete the study. The sample size was based on a within-subject variability (coefficient of variation) of 21% for the area under the concentration versus time curve (AUC) and maximum observed drug concentration (C_{max}) of dulaglutide from previous studies. Eighteen subjects will provide a 90%

probability that the half-width of the 90% confidence interval (CI) of the ratio of the geometric means for AUC and C_{\max} is no larger than 14%.

Subjects who are randomized may be replaced to ensure that at least 18 subjects may complete the study.

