9.3.2 Pharmacokinetic Statistical Methodology

The PK parameters will be summarized using descriptive statistics by treatment and also presented graphically. Mean (with and without SD bars) and individual profiles over time will be presented for PK concentrations.

The PK parameter estimates will be evaluated to determine the relative bioavailability of dulaglutide administered SC by SDP (test) compared to dulaglutide administered by PFS (reference).

Log-transformed C_{\max} and AUC(0- ∞) (primary parameters) and AUC(0-168h) and AUC(0-336h) (secondary parameters) will be evaluated in a linear mixed-effects analysis of variance model with fixed effects for treatment (SDP or PFS), period, and sequence and a random effect for subject within sequence. The ratios of least squares geometric means of SDP compared to PFS, as well as the corresponding 90% CIs, will be estimated and reported.

Example SAS code is given below:

```
proc mixed data=pk;  
class subject treatment period sequence;  
model log(pk) = treatment period sequence / ddfm=kr;  
lsmeans treatment / pdiff alpha=0.1;  
random intercept / subject=subject(sequence);  
run;
```

The t_{\max} will be analyzed nonparametrically using the Wilcoxon signed rank test. Estimates of the median difference and the corresponding 90% CIs will be calculated.

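### Does the sample-size statement (18 completers, 90% probability, half-width of 14%) overstate the precision of the planned confidence interval?

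*Protocol*

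**What the plan says.** Protocol 10.1 sets the size of the study by precision, not by power. The variability input is a "within-subject variability (coefficient of variation) of 21"% for both AUC and Cmax, taken from earlier studies. The precision claim is that "Eighteen subjects will provide a 90% probability that the half-width of the 90% confidence interval (CI) of the ratio of the geometric means" is at most 14%. Recruitment is described as "Approximately 24 subjects may be enrolled in order that at least 18 subjects complete the study", and randomized subjects may be replaced. SAP 7 repeats the claim, again as a "probability that the half-width of the 90% confidence interval (CI) of the ratio of the geometric means", without adding a scale, formula or critical value.

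The design is a two-sequence, two-period crossover. Under Protocol 7.2, "Approximately the same number of subjects will be randomized to each treatment sequence". SAP 9.3.2 analyzes log-transformed parameters in a mixed model and gives example code containing "model log(pk) = treatment period sequence / ddfm=kr" and "lsmeans treatment / pdiff alpha=0.1". That code yields a 90% interval based on the t distribution, which is then back-transformed to the ratio scale.

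**The concern.** An interval for a ratio that is back-transformed from logs is not symmetric about the estimate, so its half-width is not a unique quantity. It could be the half-width on the log scale, half the length on the ratio scale, or the distance to either limit. The critical value is also open. If one takes the SAP's t-based interval and the usual meaning of half-width, 18 completers fall 6 to 7 percentage points short of the stated 90%. This sentence is the only quantitative support for the sample size and it stands in both documents. An error in it would leave readers with an inflated idea of the precision assured at the minimum number of completers.

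**Working it through.** **Inputs**
- Completers: n = 18 (Protocol 10.1). Nine per sequence is assumed, in line with the roughly equal allocation in Protocol 7.2.
- Within-subject CV: 21% (Protocol 10.1), so the log-scale SD is σ = √ln(1 + 0.21²) = 0.2077.
- Confidence level: 90%, two-sided (Protocol 10.1; SAP 9.3.2).
- Degrees of freedom: 18 − 2 = 16, assuming complete data in both periods.

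**Formulas**
- Standard error at the assumed SD: σ√(2/n) = 0.2077 × √(2/18) = 0.0692.
- Log-scale half-width at the assumed SD: w = c × 0.0692. With c = t(0.95, 16) = 1.746, w = 0.1209. With the normal value c = 1.645, w = 0.1139.
- Probability that the observed log-scale half-width is at most h: P(χ²₁₆ ≤ 16 (h/w)²).

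**What h is when 14% is read in different ways**
- Log-scale half-width: h = 0.14.
- Half the interval length on the ratio scale, at an estimated ratio of 1: h = asinh(0.14) = 0.1395.
- Distance to the lower limit, as a percentage of the ratio: h = −ln(0.86) = 0.1508.
- Distance to the upper limit, as a percentage of the ratio: h = ln(1.14) = 0.1310.

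**Probability of meeting 14% with 18 completers**

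| Reading | t-based interval | Normal critical value |
|---|---|---|
| Distance to lower limit | 92.8% | 96.9% |
| Log-scale half-width | 83.8% | 91.4% |
| Half-length at a ratio of 1 | 83.3% | 91.1% |
| Distance to upper limit | 72.1% | 82.8% |

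Worked example, log scale with t: 16 × (0.14/0.1209)² = 21.46, and P(χ²₁₆ ≤ 21.46) = 0.838. For the lower-limit distance with t: 16 × (0.1508/0.1209)² = 24.90, and the probability is 0.928.

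**Does the plan's figure reproduce?** It does on two plausible readings, and on both 18 is the smallest n that reaches 90%:
- Lower-limit distance, t-based: 17 gives 88.9% and 18 gives 92.8%. The distance assured with 90% probability is 13.6%, which rounds to 14%.
- Log-scale half-width, normal critical value: 17 gives 87.6% and 18 gives 91.4%.

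**How large is the gap on the less favorable reading?** On the log scale with t, the half-width assured with 90% probability is 0.1209 × √(23.54/16) = 0.1466, where 23.54 is the 90th percentile of χ²₁₆. Around a ratio of 1 the limits are exp(±0.1466), about 0.86 and 1.16.

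**Sensitivity, log scale with t**
- Completers: 92.4% at 20 and 99.1% at 24.
- CV at 18 completers: 90.2% at 20%, 76.1% at 22%.
- Rounding: the documents give both inputs as whole percentages. A CV of 20.5% and a half-width of 14.49% would print as 21% and 14%, and they give 91.3%. Rounding the other way lowers the result: a CV of 21.49% with a half-width of 13.51% gives about 74%. The printed inputs therefore cannot separate 84% from 90%.

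**The case for a change.** The strongest case for acting is that the interval to be reported is known. SAP 9.3.2 points to a t-based interval, and with it both usual senses of half-width give 83% to 84%. The two routes to 90% need either a one-sided reading that the text does not mention or a critical value that the analysis will not use. The sentence carries the whole sample-size argument, and one phrase in each document would make it reproducible.

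Much of this stands. The scale and critical value are missing, and a reader who assumes a log-scale t-based half-width will not recover 90%. It does not follow that the planning figure is wrong. The code in SAP 9.3.2 is an example for the final analysis, and neither document says that the planning calculation used it. That 18 is the smallest adequate number on two readings suggests a sound calculation reported briefly. The missing definition also changes nothing later. The analysis estimates ratios with 90% intervals, there is no equivalence margin or test tied to 14%, and the precision achieved will be visible in the results whatever the planning sentence meant.

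**Conclusion.** No change follows. The statement lacks a definition, but 18 completers, 90% and 14% fit together on two reasonable readings (92.8% and 91.4%). On the log-scale reading with the SAP's t-based interval, the assurance at exactly 18 completers is about 84%, or equivalently a half-width of 0.147 where 0.14 is stated. That gap lies within the rounding of the published inputs, and it closes at 20 completers (92.4%), fewer than the roughly 24 to be enrolled. Naming the scale and critical value would be tidier, but it would alter neither the number enrolled nor the analysis nor any conclusion drawn from it. The figures assume nine completers per sequence, complete data in both periods, a true within-subject CV of 21% and, for the half-length reading, an estimated ratio of 1.
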